6.4.1 Extent of Exposure

Extent of exposure to study drug will be summarized descriptively as the duration of exposure (months), cumulative total dose received per subject (mg), actual dose intensity (mg/day), relative dose intensity (%), dose reduction, dose interruption, and dose missed per patient.

Duration of exposure (months) is determined for each patient and study medication based on dosing schedule. For daily dosing of both BGB-290 and TMZ, it will be calculated as $(\text{date of last dose} - \text{date of first dose} + 1)/30.4375$. For the dosing schedule of TMZ administered 7 days a cycle, it will be calculated as $(\text{date of last dose} - \text{date of first dose} + 22)/30.4375$. For the

dosing schedule of TMZ administered 14 days a cycle, it will be calculated as (date of last dose - date of first dose + 15)/30.4375.

Dose intensity per subject is defined for each study medication as sum of actual dose received divided by duration of treatment. Relative dose intensity is defined as total actual dose received divided by total planned dose.

The number (percentage) of patients who had missed doses, dose reductions and dose interruptions summarized. Frequency of reductions and dose interruptions will be summarized by categories (1, 2, 3, ≥ 4).

Subject data listings will be provided for all dosing records and for calculated summary statistics.

6.4.2 Dose Limiting Toxicity

Dose-limiting toxicity in the DLT evaluation period will be used to determine the dose and schedule of BGB-290 plus TMZ in the expansion cohorts. DLTs will be taken from the adverse event eCRF. Number and percentage of patients with DLT events will be listed at each combination dosing level in the DLT evaluable analysis set.

6.4.3 Adverse Events

The AE verbatim descriptions (investigator terms from the eCRF) will be classified into standardized medical terminology using Medical Dictionary for Regulatory Activities (MedDRA). Adverse events will be coded to MedDRA (Version 23.0) lower level term closest to the verbatim term. The linked MedDRA preferred term (PT) and primary system organ class (SOC) are also captured in the database.

A treatment emergent adverse event (TEAE) is defined as an AE that had an onset date or worsened during the treatment-emergent period (refer to Section 6.2.1). Treatment-related SAEs occurred after treatment-emergent period will also be counted as TEAEs. Only those AEs that were treatment emergent will be included in summary tables. All AEs, treatment emergent or otherwise, will be presented in subject data listings.

An overview table, including the incidence of and the number of subjects with TEAEs, treatment-emergent serious adverse events (SAEs), treatment-related TEAEs, TEAEs with grade 3 or above, and treatment-related SAEs will be provided. Treatment-related AEs include those events considered by the investigator to be possibly or probably related to study drug or with missing assessment of the causal relationship.

The incidence of TEAEs will be reported as the number (percentage) of subjects with TEAEs by SOC, PT and CTCAE grade. A subject will be counted only once by the highest severity grade according to CTCAE v.4.03 within an SOC and PT, even if the subject experienced more than 1 TEAE within a specific SOC and PT.

The number (percentage) of subjects with treatment-emergent SAEs, treatment-related TEAEs, TEAEs with grade 3 or above, and treatment-related SAEs will be summarized by SOC, PT and CTCAE grade. TEAEs with grade 3 or above will also be summarized by PT in descending order. Incidence of TEAEs of interest will be summarized by SOC and PT. TEAEs of interest, if needed, will be defined before database lock.

Subject data listings of all AEs, SAEs, treatment-related AEs, grade 3 or above AEs, AEs that led to death and AEs that led to treatment discontinuation, dose reduction or dose interruption will be provided.

6.4.4 Laboratory Values

Laboratory safety tests will be evaluated for selected parameters.

Laboratory parameters listed in [Table 2](#) will be graded in NCI CTCAE v4.03. A shift table (baseline grade to maximum grade after dosing on Cycle 1 Day 1) will be provided for hemoglobin, platelet count, white blood cell count, neutrophil and lymphocyte. Patient data listings of selected hematology and serum chemistry parameters, urinalysis and coagulation will be provided.

Table 2 Serum Chemistry and Hematology Laboratory Tests

Serum Chemistry	Hematology
Alkaline phosphatase (ALP)	Hemoglobin
Alanine aminotransferase (ALT)	Platelet counts
Aspartate aminotransferase (AST)	White blood cell (WBC) count
Albumin	Neutrophil (Absolute)
Total bilirubin	Lymphocyte (Absolute)
Blood Urea Nitrogen	Monocyte (Absolute)
Creatinine	Basophil (Absolute)
Sodium	Eosinophil (Absolute)
Phosphate	
Glucose	
Lactate dehydrogenase	
Total Protein	
Potassium	

6.4.5 Vital Signs

Vital sign parameters (systolic and diastolic blood pressure [BP], temperature, height and weight) will be listed by subjects and visits.

6.4.6 Electrocardiograms

During the BGB-290 PK intensive period (Day -2) and cycle 1, ECGs will be performed in triplicate on a machine provided by the sponsor. ECG findings at baseline, postbaseline will be listed by visit and/or time point. In addition, single ECG and abnormal QT interval with Fridericia's correction (QTcF) derived from triplicate ECG will also be listed.

6.4.7 ECOG Performance Status

ECOG scores and change from baseline will be listed by visit for the SAF.

7 INTERIM ANALYSIS

In dose escalation phase, before the dose is escalated to the next level, the safety review team will review the safety data to determine the next dose level. The recommended dose for dose expansion phase will be determined by the safety review team before the dose expansion phase.

Interim CSR may be conducted for the purpose of safety and/or efficacy review.

8 CHANGES IN THE PLANNED ANALYSIS

There are some changes in the planned analysis and they are listed below:

- DLT will be provided in a listing and no descriptive statistics will be provided.
- Subgroup analysis for ORR will only be done for SCLC patients in chemosensitivity and number of prior regimens.
- All by-visit analyses will be removed, and the following will be performed: hematology data will be presented in a shift table and serum chemistry will be provided in a listing. ECG will be listed. A listing of QTcF will be provided for patients with abnormal postbaseline values and abnormal changes from baseline. ECOG and vital signs will be provided in listings.
- Ninety percent CIs will be presented instead of 95% CIs.
- OS analyses will be conducted in SAF instead of Efficacy Evaluable Analysis Set. Only PFS and OS analyses will be conducted and not PFS-6m and OS-6m analyses.
- Efficacy analyses such as ORR, PFS and DOR will be based on radiographic responses or radiographic progression.
- Treatment-emergent SAEs, treatment-related TEAEs, TEAEs with grade 3 or above, and treatment-related SAEs will be summarized by SOC, PT and CTCAE grade. AEs that led

to death and AEs that led to treatment discontinuation, dose reduction or dose interruption will only be listed.

- Number of treatment cycles will not be summarized. Instead, reasons for dose reduction, dose interruption and missed dose will be summarized.

10 APPENDICES**10.1 HANDLING MISSING DATE INFORMATION**

In general, missing or partial dates will not be imputed at data level. The following rules will apply for the specific analysis and summary purposes mentioned below only.

10.1.1 Prior/Concomitant Medications, Disease and Medical History, Prior Therapy (Drug, Surgery/Procedure, Radiotherapy)

When the start date or end date of a medication/therapy/procedure is partially missing, the date will be imputed to determine whether the medication/therapy/procedure is prior or concomitant. The following rules will be applied to impute missing or partial dates for medications /therapy/procedure:

	Missing	Impute	Exception
Start Date	Day	01	N/A
	Day/Month	January 01	N/A
	Day/Month/Year or Year only	Do not impute	N/A
End Date	Day	Last day of the month	N/A
	Day/Month	December 31	N/A
	Day/Month/Year or Year only	Do not impute	N/A

If the imputed start date becomes after end date, then update start date same as end date. And if the imputed start date or end date becomes after death date, then set to death date.

For disease history, medical history and prior therapy, including initial diagnosis date, therapy date (start/end date), or surgery date, if the imputed start date or end date becomes after first dose date, then set to first dose date - 1.

10.1.2 Initial Diagnosis and Most Recent Progression

For initial diagnosis date and most recent progression date, which has no duration and only start date is available, impute the date using the following rule:

	Missing	Impute	Exception
Initial Diagnosis Date/ Most Recent Progression Date	Day	01	N/A
	Day/Month	January 01	N/A
	Day/Month/Year or Year only	Do not impute	N/A

If the imputed initial diagnosis date or most recent progression date is on or after the treatment start date, then set to treatment start date - 1.

10.1.3 Adverse Events

The imputation rule for the safety analyses will be used to address the issues with partial dates. When the start date or end date of an adverse event is partially missing, the date will be imputed to determine whether the adverse event is treatment-emergent. When in doubt, the adverse event will be considered treatment emergent by default. The following rules will be applied to impute missing or partial dates for adverse events:

	Missing	Impute	Exception
Start Date	Day	01	If Month and Year = Month and Year of treatment start date, then set to treatment start date
	Day / Month	January 01	If Year = Year of treatment start date, then set to treatment start date
	Day / Month / Year or Year only	Do not impute	If AE End Date > treatment start date, then set to treatment start date

End Date	Day	Last day of the month	N/A
	Day / Month	December 31	N/A
	Day / Month / Year or Year only	Do not impute	N/A

If the imputed AE start date becomes after AE end date, then update AE start date same as AE end date. And if the imputed start date or end date becomes after death date, then set to death date.

The following rule will be applied to impute missing toxicity grade of AE:

1. The highest grade will be used from patient's AEs with the same preferred term.
2. If patient has no AEs with the same preferred terms, the highest grade of the AEs with the same SOC will be used.
3. If patient has no same SOC, the highest grade of all AEs from that patient will be used.
4. If it is the single AE reported for that patient, no imputation for the missing grade will be done.

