10.1.1.1. Assessment of Severity

The investigator will make an assessment of severity for each AE and SAE reported during the study. AEs and SAEs should be assessed and graded based upon the NCI CTCAE v4.03.

Toxicities that are not specified in the NCI CTCAE will be defined as follows:

- Grade 1: Mild; asymptomatic or mild symptoms, clinical or diagnostic observations only, intervention not indicated
- Grade 2: Moderate; minimal, local, or noninvasive intervention indicated, limiting age-appropriate instrumental activities of daily living (ADL)
- Grade 3: Severe or medically significant but not immediately life-threatening; hospitalization or prolongation of hospitalization indicated, disabling, limiting self-care ADL
- Grade 4: Life-threatening consequences; urgent intervention indicated
- Grade 5: Death related to AE

Note: The terms “severe” and “serious” are not synonymous. Severity is a measure of intensity (for example, grade of a specific AE, mild [Grade 1], moderate [Grade 2], severe [Grade 3], or life-threatening [Grade 4]), whereas seriousness is classified by the criteria based on the regulatory definitions. Seriousness serves as the guide for defining regulatory reporting obligations from the sponsor to applicable regulatory authorities as described in Section 10.2.

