4 STUDY ENDPOINTS

4.1 PRIMARY ENDPOINTS

- Escalation: Incidence and nature of DLTs
- Escalation and Expansion: Incidence, nature, and severity of AEs, graded according to the National Cancer Institute Common Terminology Criteria for Adverse Events (NCICTCAE) v.4.03 and
- Objective response rate (ORR), as assessed using RECIST v1.1

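### SAP 10.1.3 allows a missing AE grade to be filled with Grade 5, so an ungraded non-fatal event can be tabulated as fatal

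*SAP*

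**What the plan says.** SAP 10.1.3 gives four steps for an AE with no toxicity grade:

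1. Take the worst grade among the patient's other AEs coded to that PT.
2. Failing that, take the worst grade among the patient's AEs in that SOC.
3. Failing that too, the rule reads: "If patient has no same SOC, the highest grade of all AEs from that patient will be used".
4. Only where the patient has no other AE does the grade stay missing.

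The steps run in order, so a graded AE of the same PT takes precedence over one of the same SOC, and either takes precedence over the rest. No step sets an upper limit or excludes Grade 5. No step requires the AE that lends its grade (the donor, below) to be treatment-emergent or related. SAP 6.2.2 and 6.2.3 leave missing data alone unless the SAP specifies otherwise. Section 10.1.3 is such a specification, so it governs.

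The filled grade then enters the tables of SAP 6.4.3: "The incidence of TEAEs will be reported as the number (percentage) of subjects with TEAEs by SOC, PT and CTCAE grade". The counting rule there is: "A subject will be counted only once by the highest severity grade according to CTCAE v.4.03 within an SOC and PT". The same layout is used for treatment-emergent SAEs, treatment-related TEAEs, TEAEs of Grade 3 or above, and treatment-related SAEs.

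On fatal events, Protocol 10.1.1.1 spells out a scale for toxicities that the CTCAE does not specify, and its top category is "Grade 5: Death related to AE". Protocol 10.5.5 treats death as the outcome of an event and asks for one term, that of the AE that led or contributed to it.

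**The concern.** Borrowing the worst grade is a cautious convention when the unknown is how severe an event was. Grade 5 is different in kind: it says that this particular event was linked to the patient's death. If a patient died of one AE and has another AE with no grade, the rule can attach the same death to the second AE as well. One death is then spread over several terms, and under step 3 over several organ classes. That conflicts with both protocol sections above.

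The tables affected report one of the primary endpoints, which SAP 4.1 gives as "Incidence, nature, and severity of AEs". At stake is whether a reader of the PT and SOC tables is told that a minor event was fatal. In the treatment-related tables, a patient could also be shown with a related fatal event that no investigator reported.

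**Working it through.** The plan states no figure to reproduce. The check applies the four steps literally to invented patients and then sizes one affected row.

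**Applying the rule as written**

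- *Same PT available.* Dry skin ungraded, a second dry skin AE at Grade 1, sepsis at Grade 5. Step 1 applies and dry skin becomes Grade 1. The fatal AE is not used.
- *Same SOC only.* Dry mouth ungraded, gastrointestinal haemorrhage at Grade 5. Step 2 applies and dry mouth becomes Grade 5.
- *Different SOC.* Dry skin ungraded, sepsis at Grade 5. Step 3 applies and dry skin becomes Grade 5.
- *Sole AE.* Dry skin ungraded and nothing else. Step 4 applies and the grade stays missing.

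**Which rows change when the donor is in the same table**

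Each patient counts once per SOC and PT at the highest grade (SAP 6.4.3), and the donor belongs to the same patient.

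- Step 1: donor and recipient share PT and SOC, so no row changes.
- Step 2: they share the SOC, so only the recipient's PT row changes.
- Step 3: they share neither, so one PT row and one SOC row change.
- In all three, the patient already has a Grade 5 event, so the count of patients with any Grade 5 event changes by 0.

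**Which counts change when the donor is outside the table**

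- *Unrelated donor.* Dry skin ungraded and related, sepsis at Grade 5 and unrelated. In the treatment-related table, the patient's highest grade goes from missing to 5.
- *Donor not treatment-emergent.* Dry skin ungraded and treatment-emergent, sepsis at Grade 5 and not. In the TEAE table, the highest grade goes from missing to 5. This route is narrow. Protocol 10.4.1 stops general AE reporting 30 days after the last study treatment or at new anticancer therapy, and SAP 6.2.1 counts later treatment-related SAEs as TEAEs. It could still arise because SAP 6.2.1 counts its 30 days from the last pamiparib dose, so an AE recorded after later temozolomide dosing can fall outside the window.

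**Size of one changed row**

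Shift = 1/n, where n is the number of patients in the column. Cohort sizes come from SAP 5. Dose-level sizes follow Protocol 4.2.2, whose three and six are minimums.

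- n = 25: 1/25 = 4%; n = 20: 1/20 = 5%.
- n = 6: 1/6 = 17%; n = 3: 1/3 = 33%.
- SAP 5 also gives about 200 patients in 6 cohorts, or 200/6 = 33 on average. At that size the shift is 1/33 = 3%.

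**Cap or exclusion**

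Capping the filled value at Grade 4 removes the false fatal entry, but dry skin then appears as Grade 4 on the strength of the fatal sepsis alone. Excluding Grade 5 AEs as donors leaves it missing instead.

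**The case against.** The strongest reply is that this will seldom happen and will change little. It needs an AE still ungraded at database lock and a Grade 5 AE in the same patient, with no graded AE of the same PT, or lower-graded AE of the same SOC, taking precedence. Investigators must grade every AE (Protocol 10.1.1.1), and the data are reviewed for completeness (Protocol 9.2). Deaths due solely to progression are not reported as SAEs (Protocol 10.5.4), which reduces the number of Grade 5 donors. AEs leading to death also get their own listing (SAP 6.4.3). All of this stands and keeps the point minor. The listing is only a partial safeguard: SAP 8 confirms that these AEs are listed and not tabulated, and the SAP does not say whether the listing is selected by grade or by outcome.

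A second reply is that worst-case filling matches the SAP's practice elsewhere: doubtful AEs default to treatment-emergent (10.1.3), and missing causality counts as related (6.4.3). That also stands for Grades 1 to 4. A reader might infer that a borrowed Grade 3 or 4 is false, or that step 3 must be deleted. The true grade is unknown, so the documents do not show an error there.

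Three further inferences go too far:

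- *A cohort's overall Grade 3 or above rate, or its fatal rate, rises by 4 to 5 points.* It does not when the donor is in the same table.
- *Dose escalation is affected because dose levels are small.* Escalation rests on DLTs and on data review (Protocol 4.2.2, SAP 7), and DLTs come from the AE eCRF (SAP 6.4.2). No section makes these decisions depend on tables with filled grades.
- *Severity by SOC and PT is itself the primary endpoint.* SAP 4.1 names incidence, nature and severity; SOC and PT are the display in SAP 6.4.3.

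**Conclusion.** The concern holds for Grade 5. As written, SAP 10.1.3 can show an ungraded non-fatal AE as Grade 5 in its own PT row (step 2), or in its own PT and SOC rows (step 3). Where the fatal donor is unrelated or not treatment-emergent, it can also create a false Grade 5 patient in the treatment-related or TEAE tables. Nothing else in the SAP prevents this.

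Each occurrence changes one patient in the affected row, with the sizes shown above. The conclusion assumes a literal reading of the four steps, and that Grade 5 means death related to that AE for all graded events. How often grades will be missing is not stated; low frequency is a judgement, not a documented figure. This is a minor correction to a rule that gives a wrong result in a rare case.

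**What to change.** In SAP 10.1.3, add that Grade 5 is never imputed: AEs of Grade 5 are excluded as donors in steps 1 to 3, and the search moves to the next step if no other donor is left. An AE with no remaining donor is shown in the missing category that SAP 6.2.3 already provides. Step 4 already leaves some grades missing, so the tables need that row in any case.

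The cost is one or two sentences and a small programming change; a few events would stay ungraded in the tables. Whether step 3 is kept for Grades 1 to 4 is the sponsor's choice.

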10.1.4 Deaths

In case complete death dates are not recorded, impute as follows:

- If year, month and day are all missing, then impute the death date as the last date of patient known to be alive + 1 for efficacy analyses, e.g., DOR, PFS and OS.
- If both month and day are missing, then the imputed month and day will be 01Jan or the last date of the last date of patient known to be alive + 1, whichever is later.
- If only day is missing, the death will be assumed to be on the first day of the month or the last date of patient known to be alive + 1, whichever is later.

10.1.5 New Anticancer therapy

If the start day of a subsequent anticancer therapy is incomplete or missing, impute as follows:

- if both month and day are missing,
 - 1) impute the date as 31Dec, if the year is earlier than the year of the first PD date + 1 or the treatment end date + 1, whichever is later
 - 2) impute the date as 01Jan, if the year is later than the year of the first PD date or the treatment end date + 1, whichever is later

- 3) impute the date as the first PD date + 1 or the treatment end date + 1, whichever is later, if the year is the same year of first PD date + 1 or the treatment end date + 1, whichever is later
- if only day is missing,
 - 4) impute the date as the first day of the month if year and month are available and partial new anticancer therapy date still could indicate it is at least one month later than the first PD date +1 or the treatment end date +1, whichever is later.
 - 5) impute the date as the last day of the month if year and month are available and partial new anticancer therapy date still could indicate it is at least one month earlier than the first PD date +1 or the treatment end date +1, whichever is later.
 - 6) Impute the date as the first PD date +1 or the treatment end date +1, whichever is later, if the year and month are the same year and month of first PD date +1 or the treatment end date +1, whichever is later.
 - The treatment end date refers to the last dose date of pamiparib.

10.2 CENSORING RULES

Table 3 shows the primary censoring rules for the derivation of PFS.

Table 3 Censoring Rules for Analysis of PFS

No.	Situation	Date of Progression or Censoring	Outcome
1	No baseline tumor assessments or no post baseline tumor assessment	Reference start date (e.g., C1D1)	Censored
2	Progression documented on scheduled visit or between scheduled visits	Date of first radiologic PD assessment	Progressed
3	No progression at the time of data cutoff or withdrawal from study	Date of last adequate radiologic assessment prior to or on date of data cutoff or withdrawal from study	Censored
4	Treatment discontinuation for undocumented progression	Date of last radiological assessment of measured lesions	Censored
5	New anticancer treatment started	Date of last radiological assessment of measured lesions prior to or on date of new anticancer treatment	Censored
6	Death before first PD assessment	Date of death	Progressed
7	Death between adequate assessment visits*	Date of death	Progressed
8	Death or PD after two or more consecutive missed visit**	Date of last adequate radiologic assessment before missed tumor assessments	Censored

9	A patient meets the criteria for more than 1 censoring rules above	Date of the earliest censoring date among all events	Censored
---	--	--	----------

Abbreviations: CR=complete response, PD=progressive disease, PR=partial response, SD=stable disease.

*Adequate tumor assessment is a radiologic assessment of CR, PR, SD, non-CR/non-PD or PD as determined by investigators or by IRC.

**More than one missed visit is defined if the duration between the last tumor assessment and death or PD is longer than 2 scheduled visits, which is 17 weeks (119 days).

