6.3.2 Secondary Efficacy Endpoints

- Pharmacokinetic parameters of BGB-290 and TMZ, including but not limited to C_{trough}
Refer to Section 6.3.6 for more detail.
- Disease Control Rate (DCR) by investigator

DCR is defined as the proportion of subjects with BOR of CR, PR, or stable disease (SD). Similar to ORR, two-sided binomial exact 90% confidence intervals will be calculated for DCR in each cohort. The table for DCR will be summarized in both SAF and Efficacy Evaluable Analysis Set. Patients without evaluable postbaseline tumor assessment will be considered as non-responders in the safety analysis set.

- Duration of Response (DOR) by investigator

DOR is defined as the time (month) from the date of the earliest documented CR or PR (that is subsequently confirmed) to disease progression or death due to any cause, whichever occurs earlier. The tables for confirmed and nonconfirmed DOR will be summarized in efficacy evaluable set and only responders will be included in the DOR calculation.

Kaplan-Meier method will be used to estimate DOR, and corresponding quartiles (including the median) in the responders. A two-sided 90% CIs of median will be calculated for each cohorts using generalized Brookmeyer and Crowley method (Brookmeyer & Crowley, 1982).

Censoring rule for DOR will follow PFS censoring rule mentioned in FDA Guidance for Industry Clinical Trial Endpoints for the Approval of Cancer Drugs and Biologics (2018). The censoring rules are described in Appendix 10.2.

- PFS and PFS-6m by investigator

PFS is defined as the time (months) from the date of the first dose of combination treatment to disease progression or death due to any cause, whichever occurs first. The PFS-6m is defined as the percentages of subjects who remain alive and progression-free at 6 months. PFS censoring rules are described in Appendix 10.2. If a patient meets the criteria for more than 1 censoring rule, PFS will be censored at the earliest censoring date. The tables for PFS and PFS-6m will be summarized in Efficacy Evaluable Analysis Set.

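### SAP Table 3 both censors a death before any post-baseline scan and counts it as a PFS event, and its tie-break does not put the death first

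*SAP*

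**What the plan says.** SAP 10.2, Table 3 is the derivation table for PFS. The rows that matter here are:

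- Rule 1, "No baseline tumor assessments or no post baseline tumor assessment": censored at the reference start date, with C1D1 as the example.
- Rule 4, "Treatment discontinuation for undocumented progression": censored at the last radiological assessment.
- Rule 6, "Death before first PD assessment": event, dated at death.
- Rule 7, death between adequate assessments: event, dated at death.
- Rule 8, death or PD after two or more consecutive missed visits: censored at "Date of last adequate radiologic assessment before missed tumor assessments". A footnote sets the limit at a gap of more than 119 days.
- Rule 9, "A patient meets the criteria for more than 1 censoring rules above": earliest censoring date, outcome censored.

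SAP 6.3.2 repeats the tie-break in its text: "If a patient meets the criteria for more than 1 censoring rule, PFS will be censored at the earliest censoring date". The same section counts death from any cause as a PFS event and analyses PFS in the Efficacy-Evaluable Analysis Set. Under SAP 6.1, a patient without a post-baseline scan stays in that set only if treatment stopped for clinical progression or death before a scan. Protocol 11.2.5 censors at the last tumor assessment those patients who have neither progressed nor died. SAP 10.1.4 imputes incomplete death dates for use in PFS.

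**The concern.** A patient who dies before the first post-baseline scan fits rule 1 and rule 6 exactly, and the two rows give opposite outcomes. No row or sentence says that the death takes precedence. Two careful programmers could derive different PFS from the same records. The patients affected are the ones whom the analysis set goes out of its way to keep.

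If rule 1 is followed, these patients leave the risk set at time zero and the earliest failures vanish from the estimate. That would affect the reported median and the Kaplan-Meier event-free rates at the time points in SAP 6.3.2. Duration of response is not touched by this conflict, because every responder has a post-baseline scan.

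**Working it through.** **1. Can the tie-break resolve it?** There are two ways to read rule 9.

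- Narrow reading: it ranks rows that censor. Rule 6 yields an event, so it is not ranked against rule 1 and the conflict stays open.
- Literal reading: the table's title calls all its rows censoring rules, so rule 9 covers rule 6 as well. The death is then censored at C1D1, and rule 6 is empty for unscanned patients.

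The second result contradicts the PFS definition in SAP 6.3.2, the censoring sentence in protocol 11.2.5 and the retention clause in SAP 6.1.

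**2. Overlap with rules 4 and 8.** If the patient first stopped for undocumented progression, rule 4 applies too. With no later scan, its date can only be the baseline scan, which protocol Appendix 1 Table 1 (footnote 16) allows up to 28 days before C1D1. The earliest date under rule 9 then precedes the PFS start. Rule 8 needs an earlier adequate assessment, and the footnote says "Adequate tumor assessment is a radiologic assessment of CR, PR, SD, non-CR/non-PD or PD". A baseline scan is none of these, so rule 8 supplies no date for a late unscanned death.

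**3. Size.** Let k of N patients die unscanned, with no other censoring before the last of these deaths, and let m patients be event-free just after it.

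- Deaths counted: S = m/N.
- Deaths censored at C1D1: S = m/(N−k).
- Ratio: N/(N−k). It persists, because the risk sets are identical from then on.

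| k | N = 25 | N = 20 | Shift at a true 40%, N = 25 |
|---|---|---|---|
| 1 | 25/24 = 1.04 | 20/19 = 1.05 | +1.7 points |
| 2 | 25/23 = 1.09 | 20/18 = 1.11 | +3.5 points |
| 3 | 25/22 = 1.14 | 20/17 = 1.18 | +5.5 points |

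N of 20 to 25 is the planned cohort size (SAP section 5). For scale, the 90% half-width at S = 0.5 and n = 25 is 1.645 × √(0.25/25) = 0.164.

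One illustration assumes n = 22, three unscanned deaths, and a median of 6 months after the first scan for the others. Six-month PFS is 0.55 with deaths counted and 0.63 with C1D1 censoring; the medians are 6.2 and 7.8 months.

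**4. How likely is k ≥ 1?** The documents give no rate. At an assumed chance p of dying unscanned, 1 − (1 − p)^25 is 40%, 72% and 93% for p = 2%, 5% and 10%.

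**5. Direction before the death.** Take N = 25, three progressions by day 56 and one unscanned death on day 60. Just before day 60, S is 22/25 = 0.880 with the death counted and 21/24 = 0.875 with C1D1 censoring. After day 60 it is 21/25 = 0.840 against 0.875, a ratio of 25/24.

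**6. The 119-day limit (minor).** It reproduces as 2 × 56 + 7 = 119 = 17 × 7. Protocol 7.7 allows ±7 days on each 8-weekly scan.

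- PD found on a scan: one missed visit gives a gap of 112 ± 14 = 98 to 126 days; two give 168 ± 14 = 154 to 182. Of the 15 × 15 = 225 offset pairs for one missed visit, 28 (12%) exceed 119.
- Death: if the last scan was a days off schedule, the second missed window closes 119 − a days after it. That is 126 days for a scan 7 days early, 119 on time and 112 for 7 days late.

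**The case against.** The strongest reply is that the intent is clear. The PFS definition, protocol 11.2.5 and the imputation of death dates all make death an event. Rule 7 covers deaths between assessments, so rule 6 naturally serves deaths before the first scan. SAP section 8 lists changes from the protocol and does not include censoring of early deaths. All of this stands, and a reader should not infer that the sponsor chose to censor these deaths. It does not settle the derivation, because the programmed table has no death exception in rule 1 and its tie-break can be read to favour censoring.

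The impact is also limited. PFS is secondary, no hypothesis is tested, ORR does not depend on these rules, and OS in the safety set still shows the deaths. The shifts in the table are well inside the half-width. Protocol 7.7 asks for imaging when a patient withdraws with deterioration, which should reduce the number of cases but cannot help when death comes first. These points bound the severity. They do not remove a systematic shift.

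Two stronger readings are tempting and not supported:

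- That C1D1 censoring can only raise the curve. Step 5 shows it slightly lower before the death; the inflation applies afterwards.
- That 119 days is a miscalculation to be replaced by 126. It is a one-window convention and the central value for deaths. A limit of 126 would suit PD scans, but after an on-time last scan it would count deaths at days 120 to 126, which follow two missed visits. After a scan 7 days late, the misclassified range would grow from 113–119 to 113–126.

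**Conclusion.** The contradiction between rules 1 and 6 is real and should be corrected before PFS is derived. One stated rule, if followed, gives a result that the plan's own definition rejects. Censoring k unscanned deaths inflates later Kaplan-Meier PFS by N/(N−k), or 1.04 to 1.14 for N = 25 and k = 1 to 3. This rests on an assumed k and on no other censoring before those deaths. Nothing changes in type I error, power or the primary endpoints.

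The 119-day limit merits a note only. It can censor PD found on a scan after a single missed visit (gaps of 120 to 126 days), and for deaths it errs in both directions.

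**What to change.** In SAP 10.2 and the matching sentence of 6.3.2:

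1. Restrict rule 1 to patients who lack a baseline or a post-baseline assessment and who have not died, with the death condition applying to both halves.
2. State that rule 9 operates only among rows whose outcome is censored and does not override a death counted under rule 6 or 7.
3. State how a death after rule 4 is handled, and that no censoring date may precede C1D1.
4. State the one exception to item 2: an unscanned death after two or more missed scheduled visits is censored at C1D1. This also supplies the date that rule 8 lacks.
5. Preferably, define rule 8 by counting missed scheduled visit windows from C1D1 instead of a fixed number of days.

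Separately, footnote 16 of protocol Appendix 1 Table 1 gives 12-weekly scans after the end-of-treatment visit for patients without PD, while protocol 7.7 and 8.5.2 give 8-weekly. These passages must be reconciled, because on a 12-weekly schedule one missed visit gives a gap of 168 ± 14 = 154 to 182 days, always above 119.

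The cost is SAP wording and one protocol reconciliation, with no new data. The downside is that reported PFS may be slightly less favourable.
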